## **1. SPECIFIC AIMS**

**Specific Aims.** This is the second phase of a two-part study. In the first phase (MGH IRB Protocol #2017P000404), we adapted an existing resiliency intervention, the Relaxation Response Resiliency Program (3RP), to the needs of women ages 50 and over who are living with HIV. We conducted preliminary testing of the refined group intervention via an open pilot study (N=13 enrolled) across two sites, MGH and Boston Medical Center), and conducted individual exit interviews to solicit feedback on the intervention, including experiences with the assessment protocol, intervention content, and number and duration of sessions. Data from these interviews were used to make adaptations to the manual in an iterative fashion after each of the three open pilot groups, and the final product will now be tested via a small randomized controlled trial.

Specifically, we will conduct a randomized study (N=up to 60) of the adapted 3RP intervention among groups of women living with HIV, ages 50 and over. Our primary aim is to test the feasibility and acceptability of all study procedures; we hypothesize that our protocol will be both feasible and acceptable. We will also examine data on the effect of the intervention on primary (e.g., resilience) and secondary outcomes of interest, but these analyses are purely exploratory, and we are most interested in how well our selected measures may be sensitive to change. Secondary outcomes will include changes in measures of psychosocial distress (depressive symptoms, anxiety, social support, and quality of life) and HIV / physical health outcomes (suppressed viral load, decreased symptom burden, improved cognitive and physical status). We hypothesize that participants in the treatment condition will experience greater improvements in resilience, psychosocial distress, and HIV / physical health outcomes. Data from this second phase of the study will inform the eventual development of a full-scale randomized controlled trial.

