#### Phase I open pilot study findings.

**Recruitment and screening.** Participants were recruited through community outreach, posting of IRB-approved flyers, and approaching patients at the Infectious Disease Clinic (BMC). At MGH, 19 participants were screened. 9 participants were eligible and were then consented/enrolled, although 3 of these participants were lost to follow up. At BMC, 20 participants were screened and 9 were eligible. Of these 9 participants, 4 were consented/enrolled and 5 were not consented due to lack of availability for group sessions and/or difficulty reaching via phone. 1 participant was lost to follow up due to over-commitment in research and scheduling difficulty.

**Feasibility and acceptability metrics.** 39 total participants were screened and 18 were found to be eligible (46.1%). Of these, 13 were consented/enrolled and 10 participated in the intervention (76.9%). The duration of the baseline assessment averaged 1.8 hours, ranging from 1.25 hours to 3.0 hours (N=13). Post-treatment assessments averaged 1.5 hours and ranged from 56 minutes to 1.57 hours (N=6). Exit interviews averaged 36.8 minutes and ranged from 12 minutes to 1.03 hours (N=6). Reasons for declining enrollment included work schedule, the number of group sessions, transportation cost and distance, medical reasons (e.g., surgical procedures limiting mobility), and other life circumstances. Of the 3 participants that were lost to follow-up, 2 noted that they were unable to participate due to medical reasons. Participants who have completed the intervention to date showed decreases in depressive symptoms as measured by the Center for Epidemiologic Studies Depression (CES-D) scale and increases in resiliency scores as measured by the Connor-Davidson Resilience Scale (CD-RISC). At the end of the intervention, participants reported being “very satisfied” with the program overall and stated that they would recommend it to others, although one participant noted the program was moderately burdensome as measured by the Perception of Study Assessments survey.

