### **3. RESEARCH STRATEGY**

**Overview.** The goal of this phase of the project is to conduct a randomized pilot study (N=up to 60) of an adapted mind-body resiliency intervention (3RP) among biologically-born women living with HIV, ages 50 and over. Based on exit interviews from the first phase of this study (open pilot), as well as qualitative work conducted previously with this population, we will conduct a small, randomized pilot of the intervention in groups of up to 10 women with HIV (total N=up to 60) to assess feasibility and acceptability of study procedures. Participants will be recruited from Boston-area hospitals and health care settings, including, but not limited to MGH and MGH satellite clinics, Brigham and Women's Hospital, Boston Medical Center, as well as community organizations serving individuals living with HIV. Participants will be screened for eligibility either by phone or in person by a study staff member. Eligible and interested participants will attend an individual study visit (either in person or via Zoom), during which they will sign informed consent (or provide verbal consent if the assessment is conducted via Zoom) and complete a baseline assessment. Following completion of this visit, participants will be randomized to either the intervention or control arm. The intervention groups will participate in the adapted 3RP intervention, while the control groups will participate in a supportive psychotherapy therapy program that is time-matched to the intervention. Participants will attend up to 10 group sessions (either in person or via Zoom), with opportunities to attend up to 3 make-up sessions in cases of scheduling conflict or missed sessions. At the end of the program, participants will complete a qualitative exit interview to provide feedback on the intervention (either in person or via Zoom). They will also complete a post-treatment assessment, and a 3-month follow-up assessment (either in person or via Zoom).

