### **Data analytic plan.**

Quantitative data will be entered in an on-going fashion (into REDCap data management system), and will be analyzed using SPSS, "R", and QSR NVivo qualitative software, version 9, after being thoroughly checked and cleaned as appropriate. [name] has the full support of a biostatistician ([name]) for all statistical analyses. We will compile descriptive statistics to examine intervention acceptability and feasibility as described above, as well as to examine indicators of change on measures of various psychosocial outcomes. We will compare each outcome between groups using mixed model regression analyses, with subject as a random effect. Fixed covariates will include time in study (baseline, end of treatment, 3-month follow-up) and time since diagnosis. Other covariates, such as education, socioeconomic status, and history of exposure to traumatic events will also be considered. We will consider exploratory mediational and moderational analyses, based on procedures outlined by Hayes. We will assess adherence in the active treatment arm, in particular to determine if adherence is related to change in the primary outcome. We will perform exploratory multivariate analyses among the outcomes, including graphical methods and the calculation and testing of correlations and partial correlations. We will examine patterns in missing data in order to see if missingness is related to measured patient characteristics. We will adjust for missing data using multiple

imputation as appropriate. We will adjust for multiple comparisons using the method of Hothorn, Bretz and Westfall. Statistical analyses will be performed using “R” software.

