## STATISTICAL ANALYSIS PLAN

## Statistical Plan for Analyses

Power: PAR-14-182 states, "...the R34 should ... enhance the probability of reaching more definitive outcomes in a larger trial... by working out the details of the experimental protocols, including the assessment protocol, the...intervention protocol, as well as the comparison intervention protocol and randomization procedures; examining the feasibility of recruiting and retaining participants into the study conditions; ... collection of preliminary data regarding feasibility, acceptability, safety, tolerability, and target outcomes is appropriate. Given the limited sample sizes that can be supported under this...mechanism, proposing the use of a comparison group for conducting fully powered tests of outcomes (i.e., efficacy) or attempting to utilize the highly variable point estimate of an effect size for power calculations would not be appropriate." As stated in the specific aims, we aim to test the feasibility and acceptability of all study procedures as a primary goal; we will not attempt to use our data to estimate an effect size. We are interested in the sensitivity of our selected measures to detect change. Thus, as an exploratory outcome, we propose to examine the intervention effect of resilience and other secondary outcomes. We have conducted power calculations to ensure any lack of effect would be unrelated to power. We also explored current funded R34 studies of similar scope that are currently funded by NCCIH, and our sample size is well within the range of what is documented in these studies (e.g., 5R34AT008423, 1R34AT007935).

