Power calculations are based on samples of older, HIV-infected women when available. When data from older HIV-infected women were not available, data from samples of older women, women, or HIV-infected populations were used. We also examined data from community samples. We calculated power estimates for the primary outcome (resilience as measured by the CD-RISC) and for two of the secondary outcomes, depressive symptoms and health related quality of life. With respect to resilience, from Dodding et al., we estimate the standard deviation of change due to the intervention to be 11.8. With 30 patients per group, we will have 80% power to detect a change in resilience of 6.2 points or greater, in absolute value, based on a paired t-test at the 0.05 two-tailed significance level. We estimate the population mean and standard deviation to be approximately 76+/-13 for community-based controls, and 71.7+/-12.5 for a community-based sample of post-menopausal women with sub-clinical depression (N=401). A change of 6.2 points corresponds to approximately 1/2 of a standard deviation for both of these populations (i.e., an effect size of 0.5). Comparing the post-pre differences between treatment arms, we estimate that we will have 80% power to detect an absolute difference of 8.7 on the CD-RISC, based on a two-sample t-test at the 0.05 two-tailed significance level (an effect size of 0.7, which corresponds to a medium-large effect size.

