For depressive symptoms, Ickovics et al. reported that 42% of HIV seropositive women were depressed, based on reporting a CES-D score of >16 for 75% of more of study visits. Assuming that the population proportion of participants with elevated depressive symptoms in the placebo arm at the end of the study is 0.42, then with 30 participants per arm, we will have 80% power to detect that the corresponding treatment proportion is <0.12 or >0.76. For health related quality of life, Mrus et al. reported a mean for the overall health domain of HRQoL in women engaged in HIV treatment of 71.4, with a standard deviation of 13.8. Using this standard deviation, with 30 participants per arm, we will have 80% power to detect if the absolute mean between-group difference in this quality of life measure at the end of the study is 10.2 points or greater, based on a two-sample t-test at the 0.05 two-tailed significance level. In summary, we are confident that we can achieve a medium to large effect size across multiple outcomes with the proposed N.

**Analyses:** With respect to quantitative data, we will compare each outcome between groups using mixed- model regression analyses, with subject as a random effect. Fixed covariates will include time in study (baseline, end of treatment, 3 month follow-up) and time since diagnosis. Other covariates, such as education, socioeconomic status, and history of exposure to traumatic events will also be considered. We will consider exploratory mediational and moderational analyses, based on procedures outlined by Hayes. We will assess adherence in the active treatment arm, in particular to determine if adherence is related to change in the primary outcome. We will perform exploratory multivariate analyses among the outcomes, including graphical methods and the calculation and testing of correlations and partial correlations. We will examine patterns in missing data in order to see if missingness is related to measured patient characteristics. We will adjust for missing data using multiple imputation as appropriate. We will adjust for multiple comparisons using the method of Hothorn, Bretz and Westfall. Statistical analyses will be performed using “R” software.

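### Women in both arms are treated in therapy groups, but the between-arm model and the power figures treat them as independent

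*Combined protocol and SAP*

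**What the plan says.** Section 3 (Research Strategy, Overview) plans a randomized pilot "in groups of up to 10 women with HIV (total N=up to 60"). The comparator is also delivered in groups: "the control groups will participate in a supportive psychotherapy therapy program that is time-matched to the intervention". Under Study procedures and data collection, women are randomized 1:1 as individuals after the baseline visit. Control make-up sessions are individual, and women may join up to three group sessions by phone.

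The protocol's data analytic plan states: "We will compare each outcome between groups using mixed model regression analyses, with subject as a random effect". The SAP (Analyses) has the same model, with "model regression analyses, with subject as a random effect". The fixed covariates named are visit and time since diagnosis, and the further covariates to be considered are all patient characteristics. Neither text mentions therapy group, facilitator, ICC, design effect or cluster-robust errors.

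On power, the SAP says "we will have 80% power to detect an absolute difference of 8.7 on the CD-RISC", using a two-sample t-test with 30 women per arm. It gives the reason for the calculation: "We have conducted power calculations to ensure any lack of effect would be unrelated to power". The Specific Aims say of the outcome comparisons that "these analyses are purely exploratory".

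**The concern.** Women in one therapy group share members and sessions for up to ten meetings, and the programme works directly on social support, stigma and isolation. Their outcomes may therefore resemble each other more than those of women in different groups. A subject random effect links one woman's three visits. It does nothing for correlation between different women.

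If that correlation is positive, the standard error of the between-arm difference is too small. A positive finding would then look firmer than it is. A null resilience result would be read against an assurance of adequate power that the design does not deliver. The planned multiplicity adjustment does not help, because it corrects for the number of tests and not for an understated standard error.

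**Working it through.** **Inputs from the SAP power text.** 30 women per arm; SD of CD-RISC change 11.8; difference 8.7; quality-of-life SD 13.8 and difference 10.2; two-sided 0.05.

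**Inputs that must be assumed.** The documents give no ICC, so I use 0.02, 0.05 and 0.10. They give no expected group size, only the ceiling of 10. The Phase I open pilot had three groups; "13 were consented/enrolled and 10 participated in the intervention (76.9"%), which is 10/3 = 3.3 to 13/3 = 4.3 women per group. I use m = 3.3, 4.3, 5 and 10.

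**Step 1: the plan's own figures.** The noncentrality is difference / (SD × √(2/30)), on 58 df.
- CD-RISC: 8.7 / (11.8 × 0.2582) = 2.856, power 80.2%. The exact 80% detectable difference is 8.68.
- Quality of life: 10.2 / (13.8 × 0.2582) = 2.863, power 80.4%.

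Both match the stated 80% with a design effect of exactly 1, so no allowance was made for grouping.

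**Step 2: type I error of the analysis that ignores groups.** The design effect is DE = 1 + (m − 1) × ICC. The true error of a nominal 5% test is about 2 × [1 − Φ(1.96/√DE)]. For m = 10 and ICC 0.05, DE = 1.45 and √DE = 1.20, so 1.96/1.20 = 1.63 and the error is 10.4%.

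| Group size | ICC 0.02 | ICC 0.05 | ICC 0.10 |
|---|---|---|---|
| 3.3 | 5.5% | 6.4% | 7.8% |
| 4.3 | 5.8% | 7.0% | 9.0% |
| 5 | 5.9% | 7.4% | 9.8% |
| 10 | 7.1% | 10.4% | 15.5% |

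Simulating a t-test on change scores that ignores groups (100,000 trials per setting) agrees. At ICC 0.05 it gives 7.3% (groups of 5) and 10.4% (groups of 10). At ICC 0.10 it gives 9.8% and 15.9%. At ICC 0 it gives 5.0% and 5.1%.

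**Step 3: power for 8.7 points at ICC 0.05, design effect only.** Replace the SD by SD × √DE and keep 58 df. The detectable difference is 8.68 × √DE.

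| Group size | DE | Power | 80% detectable difference |
|---|---|---|---|
| 3.3 | 1.117 | 75.7% | 9.2 |
| 4.3 | 1.167 | 73.9% | 9.4 |
| 5 | 1.20 | 72.7% | 9.5 |
| 10 | 1.45 | 64.5% | 10.5 |

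For the 10.2-point quality-of-life difference, power is 72.9% (groups of 5) and 64.7% (groups of 10).

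**Step 4: the separate cost of few groups.** A group-level t-test with k groups per arm has 2k − 2 df. Power for 8.7 points is:
- 6 groups of 5 per arm (10 df): 73% at ICC 0 and 65% at ICC 0.05.
- 3 groups of 10 per arm (4 df): 58% at ICC 0 and 44% at ICC 0.05.

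This loss arises even with no clustering. It is the price of a valid test with few groups.

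**The case against.** The strongest reply is that little rests on these p-values. The comparisons are exploratory, the primary aim is descriptive, the SAP says the data will not be used to estimate an effect size, and no progression rule depends on them. That stands, and it limits the seriousness. It does not rescue the SAP's assurance about power, nor the tests planned at two-sided 0.05 with a named multiplicity method.

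The size is also assumed. Ten is a ceiling, and Phase I groups were much smaller. At 3.3 per group and ICC 0.02, type I error is 5.5% and power 78%, close to nominal. With 7 to 9 groups per arm (30/4.3 to 30/3.3), a group-level test at ICC 0 keeps about 75–76% power, better than the 58–73% in Step 4. Individual make-ups and phone-in sessions may lower the correlation further. All of this is fair, but the plan has no means of showing which case applies.

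Two other weaknesses in the power text are real but separate:
- It assumes no dropout. At the Phase I participation rate, 30 × 10/13 ≈ 23 women per arm, and power for 8.7 points is about 69% before any clustering.
- The protocol describes a 10-item CD-RISC scored 0–40, while the power text cites means of 76 and 71.7, which cannot occur on that scale. The point differences in Step 3 therefore inherit an unresolved scale. The design effects and type I errors do not depend on it.

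Finally, the calculations use a t-test on one change score, not the three-visit mixed model with covariates and imputation. The direction carries over, but the exact percentages are approximate.

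**Conclusion.** The concern holds. Both arms are delivered in groups, subject is the only random effect, and the power figures match independent women exactly. Whenever the within-group ICC is above zero, the model as written gives standard errors that are too small, and the stated 80% power is not delivered.

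At an assumed ICC of 0.05, type I error is about 6.4% to 10.4%, and power for 8.7 points about 76% down to 65%, for groups of 3.3 to 10. At ICC 0.02 with small groups the effect is slight. At ICC 0.10 with full groups, type I error is about 16%. These figures rest on the assumed ICC and group sizes, 30 women per arm and the plan's SD of 11.8. The point should be fixed because it affects the exploratory comparisons and the power assurance. It does not affect the feasibility and acceptability aim.

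**What to change.** - **Record therapy group and facilitator for every woman.** This comes first, because without it no grouped analysis is possible later. Analyse each woman in her assigned group, whatever make-up or phone-in sessions she used. For a woman who repeats consent and baseline before joining a later group, that is the group she finally joins.
- **Add a random effect for therapy group**, nested in arm and acting on post-baseline visits, in both the protocol's and the SAP's model. Use Satterthwaite or Kenward-Roger degrees of freedom, and state how these combine with multiple imputation and the planned multiplicity adjustment.
- **State in advance what is done if the group variance is estimated at zero.** In simulation at a true ICC of 0.05, an ANOVA estimate was zero or negative in 38% of trials (6 groups of 10 in total) or 36% (12 groups of 5).
- **Report the ICC with its interval as a rough estimate only**, not as a planning value. The median 95% interval in those simulations ran from −0.06 to 0.50 and from −0.11 to 0.37.
- **Restate the power paragraph** over a range of ICCs and group sizes, and qualify the sentence that links any lack of effect to adequate power.

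The cost is one model term in R with its degrees-of-freedom rules, two recorded variables and two rewritten power sentences. No extra participants are needed. The downsides are wider intervals, few degrees of freedom, a group variance that may collapse to zero, and a less favourable stated power.

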### **Mechanisms for reporting adverse events.**

Adverse events are defined as harmful occurrences to study participants, either study related or non-study related, during participation in the clinical intervention study. As a result of participation in the intervention or qualitative interviews, study staff may become aware of an adverse event, including participant distress or disclosure of violence or abuse, or suicidal ideation. Study staff will be trained to make appropriate referrals for clinical care in consultation with the PI and co-investigators. All adverse events will be reported by the PI to the IRB within the required reporting periods as outlined by the PHRC policy, and these will be discussed during team meetings. Anticipated or unrelated adverse events will be reported to the DSMB and the annual summary, the DSMB report will state that the board has reviewed all AE reports. These will be discussed on weekly calls / in-person meetings with [name] and key study staff. Unexpected fatal or life-threatening AEs related to the intervention will be reported to the NCCIH Program Officer within 7 days. Other serious and unexpected AEs related to the intervention will be reported to the NCCIH Program Officer within 15 days. To ensure confidentiality during reporting, adverse event reports and annual summaries will not include identifiable information. Each report will only include the participants' ID numbers.

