Following completion of the intervention or the control group sessions, participants will complete a post-treatment assessment (either in person or via Zoom). Apart from the sociodemographic information, participants will complete all the same quantitative self-report measures (described below) as in the baseline assessment. Additional measures assessed at post-treatment include a measure of client satisfaction and a measure of perceptions regarding study assessments. All questionnaires will be completed on either a touchscreen tablet or on paper as described above (if the assessment is conducted in person) or verbally via phone or directly in REDCap (if the assessment is conducted via Zoom). We will also conduct semi-structured, individual qualitative exit interviews (either in person or via Zoom) to evaluate participants' perceptions of their experience in the study. Interviews will explore treatment content, satisfaction with group format (including group versus individual delivery), length of individual sessions, scheduling and location of sessions, adherence to the skills covered in the sessions, length of the overall group intervention, and perceptions of the assessment experience, including length of battery. In

addition to the qualitative interviews, the randomized pilot trial will provide information relevant to manual revisions in the form of audio recordings of sessions, weekly progress notes, therapist and patient ratings of satisfaction with and helpfulness of treatment procedures, and participant ratings of out of session practice of skills. Audio recordings of selected sessions will be made available for download from a secure, password-protected, HIPAA-compliant website and viewed by the study team.

Finally, we will conduct 3-month follow-up assessments (either in person or via Zoom), during which participants will complete all the same quantitative self-report measures (described below) as in the post-treatment assessment, apart from the sociodemographic information, client satisfaction measure, and measure of perceptions regarding study assessments. All questionnaires will be completed on either a touchscreen tablet or on paper as described above (if the assessment is conducted in person) or verbally via phone or directly in REDCap (if the assessment is conducted via Zoom).

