### **Participant remuneration.**

Participants will receive up to \$293 over the course of the study, including \$25 for their time after each of the assessment visits (i.e., baseline, post-treatment, 3-month follow-up, and optional qualitative exit interview), \$25 for interview questions related to COVID-19, as well as \$12 reimbursement for attending all study visits (either in person or via Zoom).

Participants may be remunerated via eCheck or Forte cards. If study visits are conducted virtually, Forte cards will be mailed to participants' homes for the purposes of remuneration during the study.

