### **Minimization of risks.**

It is unlikely that participants will be at any risk for physical harm resulting from study participation. In the event that any study procedures result in significant distress, the participant will be given the opportunity to cease study participation. All research study staff will be thoroughly trained in assessment procedures. If a participant is determined to be in distress or actively suicidal and at risk for self-harm during any study procedure, study staff will contact the PI ([name]) or another trained clinician, so that appropriate clinical intervention is executed. Any participant who scores greater than or equal to a 23 on the CES-D will be evaluated (either in person or via Zoom) by a licensed psychologist or another qualified provider/clinician and referred for additional services as needed. The group facilitators will participate in regular supervision. We have added a DSMB that will convene at least annually to afford additional, external review of study procedures, participant safety, and adverse events.

Additionally, [name] has been involved with numerous local and national studies of persons with HIV and has considerable experience implementing measures to protect confidentiality. Some of these steps include in-service trainings on confidentiality and the assignment of study ID numbers. Staff at all sites who conduct participant recruitment, screening, enrollment, and assessments will have been trained in ethical human subjects research, screening and interviewing techniques, to minimize participant risk as much as possible; this includes all staff at non-Partners sites. All data will be kept confidential, under lock-and-key, accessible only to trained study staff. Participants' data will be identified by an ID number only, and a link between names and ID numbers will be kept separately under lock and key. Any paper-based assessments will be stored under lock and key within a secure office space accessible only to approved study staff. The study database will be secured with password protection and accessible only to approved study staff. Participants will be asked to sign a confidentiality statement prior to the inception of group sessions (if the baseline assessment is conducted in person) or verbally consent to such an agreement (if the baseline assessment is conducted via Zoom).

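### No structured adverse-event question is specified at any visit, so beyond CES-D screening and observed distress, recording depends on staff happening to learn of events

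*Combined protocol and SAP*

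**What the plan says.** **Definition.** Under Mechanisms for reporting adverse events, harms count when they are "either study related or non-study related, during participation in the clinical intervention study". The section names participant distress, disclosure of violence or abuse, and suicidal ideation as examples. It gives no start or end date for collection.

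**Capture.** The same section states the route as "As a result of participation in the intervention or qualitative interviews, study staff may become aware of an adverse event". The rest concerns referral and onward reporting to the IRB, the DSMB and the funder, with 7-day and 15-day limits for certain events.

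**Exit interview.** Participant remuneration lists the paid visits as "baseline, post-treatment, 3-month follow-up, and optional qualitative exit interview". The Overview of Research Strategy reads as though every participant will do the interview, so its status is not settled.

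**Other safety routes.** Minimization of risks sends any participant with a CES-D score of 23 or more for clinician evaluation. It also has staff call in a clinician "If a participant is determined to be in distress or actively suicidal and at risk for self-harm during any study procedure".

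**Visits.** On the last visit the protocol says "Finally, we will conduct 3-month follow-up assessments (either in person or via Zoom), during which participants will complete all the same quantitative self-report measures". That battery includes the CES-D and the symptom distress module. No AE item is described for it, or for the post-treatment visit.

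**Leavers.** Retention promises efforts to keep in touch with women who stop the intervention but will still do assessments. Feasibility tracks reasons for leaving early and does not link them to AE reporting.

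**SAP.** It quotes the funding announcement: "collection of preliminary data regarding feasibility, acceptability, safety, tolerability, and target outcomes is appropriate". It contains no AE summary.

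**The concern.** The definition is wide and the stated means of finding events is narrow. Reporting deadlines and DSMB review can act only on events that someone has recorded. If nobody asks, the record depends on what a woman volunteers and on whether staff are in contact with her when she might do so.

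The weak spots are predictable. Group contact ends after the sessions, women who leave have less contact still, and new illness, injury, violence or abuse is not something the described questionnaires ask about after baseline. The DSMB would then review a count of unknown completeness, and the pilot would hand the later full-scale trial safety data of limited use.

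**Working it through.** The plan gives no AE rate or detection figure, so there is no plan figure to reproduce. The check sets each type of event against the routes described in the text.

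**1. Routes by type of event**

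| Type of event | Routes described | Gap |
|---|---|---|
| Depressive symptoms | CES-D at baseline, post-treatment and 3 months, both arms, with evaluation at 23 or more | Not stated that a triggering score is recorded as an AE |
| Distress or suicidality | Escalation during any study procedure, which includes assessment visits | Depends on staff noticing; questionnaires may be entered directly in REDCap when the visit is by Zoom |
| Listed physical symptoms | Symptom distress module, 20 symptoms, past four weeks | Not described as an AE source; short recall |
| New illness, injury or hospital admission | Staff awareness | No question described at any visit |
| New violence or abuse | Staff awareness | Trauma history is taken at baseline with the sociodemographic data, which later visits omit |

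The COVID-19 items ask about the effect of the pandemic and are not described as an AE enquiry.

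**2. Contact after post-treatment.** Remuneration: maximum $293 = 4 × $25 (three assessments and the exit interview) + $25 (COVID-19 questions) + 14 × $12. Check: 100 + 25 + 168 = 293. Fourteen visits fit 10 sessions + 3 assessments + 1 exit interview. On that reading, the 3-month visit is the one scheduled contact after the post-treatment assessment and exit interview.

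**3. Recall.** Taking 3 months as 13 weeks (an assumption), the symptom module's four weeks cover 4/13 = 31% of that interval, and only for its 20 listed symptoms.

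**4. What partial detection would do (illustration, assumed rates).** Let r be the true proportion of women with an event, d the chance that it is detected, and 30 the arm size used in the SAP's power section. Expected number seen = 30 × r × d. P(at least one seen) = 1 − (1 − r × d)^30. The values of d borrow Phase I proportions as a plausible range, not as estimates of detection: 10/13 = 77% of those enrolled took part; exit interviews had reached 6/10 = 60% of those who took part and 6/13 = 46% of those enrolled, with collection still under way.

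| r | d = 100% | 77% | 60% | 46% |
|---|---|---|---|---|
| 5%: expected | 1.50 | 1.16 | 0.90 | 0.69 |
| 5%: P(≥1) | 78.5% | 69.2% | 59.9% | 50.2% |
| 10%: expected | 3.00 | 2.31 | 1.80 | 1.38 |
| 10%: P(≥1) | 95.8% | 91.0% | 84.4% | 75.7% |
| 20%: expected | 6.00 | 4.62 | 3.60 | 2.76 |
| 20%: P(≥1) | 99.9% | 99.3% | 97.8% | 94.5% |

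At a true rate of 5%, an arm with no recorded event has probability 100 − 78.5 = 21.5% under full detection and 100 − 50.2 = 49.8% at 46% detection. A blank record would then say little.

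**The case against.** The strongest reply is that safety is not left to chance. CES-D evaluation and escalation of distress operate in both arms and at the 3-month visit, so two of the event types named in the AE section have a route there. Women who stop sessions are still sought for assessments by someone other than their facilitator, and their reasons for leaving are recorded. The protocol judges physical harm unlikely, the primary aim is feasibility and acceptability, and no between-arm safety test is planned. The words on safety and tolerability in the SAP are the funder's. Table 4, the assessment timeline, is not in the text available and might list an AE item.

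Most of this stands, and it limits the point. It does not supply a question about new medical events, violence or abuse, and it does not tie reasons for leaving to the AE definition.

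Three stronger readings are tempting and are not supported:

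- **Sessions and interviews are the sole routes, so the months after sessions are unmonitored.** Minimization of risks contradicts this. A share of weeks without enquiry is also not a meaningful measure: no scripted AE question is described for the sessions either, and a question at 3 months can look back.
- **AE counts will differ by arm because of contact.** Sessions are matched for number and length. Control make-up sessions are individual therapy, but the intervention format is not stated, so no contrast can be drawn. Mailed practice notes go to the intervention group when sessions are virtual, but nothing shows that they reveal AEs. If detection were 80% in one arm and 60% in the other (assumed), equal true rates would give an apparent ratio of 0.80/0.60 = 1.33. That shows what could happen, not what will.
- **Phase I drop-outs can be scaled to this trial as missed AEs.** The text says "Of the 3 participants that were lost to follow-up, 2 noted that they were unable to participate due to medical reasons". Being unable to take part may reflect an existing condition, and 10 of the 13 enrolled took part, which suggests that these women may never have started.

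**Conclusion.** The point holds as a gap in ascertainment. The available text specifies no structured AE enquiry at any visit. Outside the CES-D evaluation and distress or suicidality observed during a procedure, events meeting the protocol's own definition enter the record if staff happen to hear of them. New medical events and violence or abuse are the most exposed, chiefly between post-treatment and 3 months and in women who stop sessions or, above all, assessments.

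The number missed cannot be derived from the documents; the table of assumed rates shows the direction and a plausible range only. Bias between arms remains a possibility. The conclusion assumes that Table 4 holds no AE item. If it does, the point reduces to a missing cross-reference, the undated window and the absent listing. For a small behavioural pilot this is a worthwhile, inexpensive improvement and not a flaw that undermines the primary aim.

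**What to change.** - **Mechanisms for reporting adverse events:** add a short scripted AE question, worded identically in both arms, covering the events that the section names and new medical problems. Have the non-facilitator assessor already required under Assessment instruments ask it at the post-treatment and 3-month visits and, by phone where possible, at withdrawal.
- **Window:** state that collection runs from consent to the 3-month visit.
- **Feasibility:** review each recorded reason for leaving against the AE definition, and log those that meet it.
- **SAP and DSMB report:** add a descriptive by-arm listing, with women affected and number of events, and no test.
- **Table 4:** if it already holds an AE item, refer to it from the AE section.

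The cost is protocol wording, a few minutes at visits already scheduled, a call to women who withdraw, and one listing. More events will be recorded and reported, most of them probably unrelated to the study. No extra visit is needed.
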